- In contrast grade B fistulae require a change in clinical management; patients are made NPO (nothing by mouth) and supported with enteral or parenteral nutrition. They require leaving pancreatic drains in place and will often necessitate a delay in discharge.
- In patients with a grade C fistula, major deviations in management are required. These patients may not be clinically stable and require aggressive interventions including care in the intensive care, nothing by mouth, supplemental nutrition, intravenous antibiotics and percutaneous drainage with a possible return trip to the operating room for repair, creation of a new

anastomosis between the pancreas and the gastrointestinal tract, or completion pancreatectomy [7].

Superficial and organ space infections are defined as follows from pre-existing definitions in the literature [6]:

Superficial infections will be defined as an infection which occurs within 30 days after surgery and involves either skin/subcutaneous tissue (superficial) or the fascial/muscle layer (deep) of the incision. Furthermore, the patient will need to meet at least one of the following criteria:

1. Purulent drainage from the incision but not from the organ/space component of the surgical site;
2. Organisms isolated from an aseptically obtained culture of fluid or tissue from the superficial incision;
3. At least one of the signs or symptoms of infection, including pain or tenderness, localized swelling, redness and heat and a superficial incision deliberately opened by a surgeon and either found to be culture-positive or not cultured (a culture-negative finding did not meet this criterion);
4. A deep incision spontaneously dehisced or deliberately opened by a surgeon and either found to be culture-positive or not cultured (a culture-negative finding did not meet this criterion) and at least one of the signs or symptoms of fever ($>38^{\circ}\text{C}$), localized pain or tenderness;
5. An abscess or other evidence of infection involving the deep incision found on direct examination, during reoperation, or by histopathologic or radiologic examination.

Organ space infections will be defined as infections that occur within 30 days after surgery that is related to the surgery and involves any part of the body excluding that skin, fascia, or muscle layers, and meets at least one of the following criteria:

1. Purulent drainage from a drain that was placed through a stab wound into the organ or space;

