9.0 Statistical Considerations

The patients' characteristics will be summarized by treatment arms and compared using two-sample t-tests for continuous and Chi-square test for categorical variables as appropriate. Nonparametric tests will be used if there is a normal distribution assumption violation. All analysis will be performed using SAS 9.3 (Cary, NC)

Efficacy in reducing superficial and organ space infections. In the primary analysis, proportion of patients with infection will be tabled and calculated for each arms and compared using a Chi-square test. In the secondary analysis, we will also use a logistic regression model with infection as the outcome variable, treatment arm as the main predictor, and will adjust for disease process in order to further evaluate the efficacy.

Efficacy in reducing pancreatic fistula rates will be analyzed in a similar way to the primary outcome variable.

Toxicity data related to the treatment will be summarized by treatment arm.

Early Stopping Rule:

An interim analysis will occur after 82 patients have been treated. Overall complication rate and rate of major complication (e.g. Grade 3 through 5) will be analyzed for each treatment group at the interim analysis. If the placebo group infection rate is three (3) times the infection rate of the treatment group, the study will be stopped.

Sample Size and Statistical power: Historical data in hepatopancreatobiliary surgery show that the treated group will reduce primary outcome rate from 24% to 8%. The anticipated reduction in infectious complications was estimated based on historical outcome data for abdominal operations involving one or more gastrointestinal anastomoses. Using a two-sided Chi-square test, we will need 82 patients in each arm to detect such a difference with 80% power and 5% Type I error rate. With no attrition rate, we will need to recruit 164 patients totally. The power analysis was performed for the primary endpoint only.

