11.0 DATA SAFETY MONITORING PLAN

DSMP for Moderate Risk Trials (Level 2)

Moderate Risk Trials

Investigators will conduct continuous review of data and patient safety. **Monthly review meetings** for Phase I/II and Phase II trials are required and will include the principal investigator, clinical research specialist and/or research nurse (other members per principal investigator's discretion). **Monthly** meeting summaries will include review of data, the number of patients, significant toxicities as described in the protocol, and responses observed. Summaries will be submitted monthly and reviewed quarterly by the DSMC.

Study Auditing and Monitoring

All trials conducted at the IUSCC are subject to auditing and/or monitoring. Reports will be reviewed quarterly by the full DSMC (Reference Risk Table in full DSMC Charter).

Early Study Closure

At any time during the conduct of the trial, if it is the opinion of the investigators that the risks (or benefits) to the patient warrant early closure of the study, this recommendation will be made in writing to the Data Safety Monitoring Committee. Alternatively, the DSMC may initiate suspension or early closure of the study based on its quarterly review of the investigator reports.

Reporting Guidelines

The DSMC has streamlined the reporting process by utilizing reports from OnCore. This has allowed direct view of reports within the Clinical Trials Management System (CTMS); thus discontinuing paper reports. SAE reports are entered into OnCore monthly and reviewed by the DSMC chair and/or coordinator monthly. Findings will be reported to the full DSMC quarterly.

Reporting Death:

Death will be reported per local IRB reporting guidelines. The DSMC will review all reported deaths monthly.

Study Accrual Oversight

Accrual data will be entered into the IU Simon Cancer Center OnCore system on a monthly basis. The Protocol Accrual Committee (PAC) reviews study accrual twice per year while the PAC coordinator reviews accrual quarterly.

Protocol Deviations

Protocol deviations are entered into OnCore monthly and reviewed by the DSMC chair and/or coordinator monthly. Findings will be reported to the full DSMC quarterly.

12.0 References:

1. Yeo, C.J., et al., *Six hundred fifty consecutive pancreaticoduodenectomies in the 1990s: pathology, complications, and outcomes*. Ann Surg, 1997. **226**(3): p. 248-57; discussion 257-60.

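### The interim rule stops the trial when the observed infection ratio is 3, which is the design effect itself, with no test, minimum event count or alpha allocation, so the stated 5% type I error is not held (about 5.4% to 6.5%)

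*Combined protocol and SAP*

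**What the plan says.** All of the design statements are in Section 9.0, Statistical Considerations.

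- **Timing of the look:** "An interim analysis will occur after 82 patients have been treated".
- **Stopping rule:** "If the placebo group infection rate is three (3) times the infection rate of the treatment group, the study will be stopped". The overall and Grade 3 to 5 complication rates are also to be looked at by group, but no threshold is attached to them.
- **Primary analysis:** "proportion of patients with infection will be tabled and calculated for each arms and compared using a Chi-square test".
- **Sample size:** the primary outcome rate is assumed to fall from 24% to 8%, and "we will need 82 patients in each arm to detect such a difference with 80% power and 5% Type I error rate". Attrition is taken as zero, for a total of 164.

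Section 8.0 gives the endpoint a 30-day window: "Superficial infections will be defined as an infection which occurs within 30 days after surgery". Organ space infections have the same window. Under Early Study Closure in Section 11.0 (Data Safety Monitoring Plan), the investigators may recommend closure, and "the DSMC may initiate suspension or early closure of the study based on its quarterly review of the investigator reports". That section sets no statistical boundary.

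**The concern.** The rule is mandatory and acts on the primary endpoint, so it cannot be set aside as a safety look. It is a second chance to end the trial in favour of treatment, and nothing in the plan pays for that chance.

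A ratio of two observed rates also says nothing about precision. At 41 patients per arm, a ratio of 3 can rest on a handful of infections.

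The rule is not fully specified either. It does not say whether a ratio above 3 counts, whether exactly 3 is enough, or what happens when the treated arm has no infections. Nor does the plan say how a stopped trial will be analysed. Two monitoring committees could apply it differently to the same table.

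At stake are the stated 5% error rate, possibly the stated 80% power, and whether a trial stopped at half size could support a conclusion under its own primary test.

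**Working it through.** **1. Reproducing the plan's sample size.** Inputs from Section 9.0: 24% and 8%, two-sided 5%, 80% power. With p̄ = (0.24 + 0.08)/2 = 0.16 and a difference of 0.16, the pooled-variance formula without continuity correction is

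n = [1.960·√(2·0.16·0.84) + 0.8416·√(0.24·0.76 + 0.08·0.92)]² / 0.16²
= [1.960·0.5185 + 0.8416·0.5060]² / 0.0256 = 1.4420² / 0.0256 = 81.2, so 82 per arm.

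This matches the plan. The continuity-corrected formula gives 94, so the uncorrected chi-square is used below.

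**2. The trigger.** 24%/8% = 3, the same as the stopping ratio.

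**3. Evidence needed to stop.** Assume 41 per arm at the look (1:1 blocked allocation, 82/2). For 2 treated v 7 placebo infections, the pooled rate is 9/82 = 0.1098 and the difference is 5/41 = 0.1220. The standard error is √(0.1098·0.8902·2/41) = 0.0690, so Z = 1.77 and p = 0.077. The ratio is 3.5, so the trial stops under either reading. If exactly 3 is enough, these tables also stop it:

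- 1 v 3: p = 0.31
- 2 v 6: p = 0.14
- 3 v 9: p = 0.061

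**4. Type I error.** All binomial outcomes at 41 per arm were enumerated and the stop rule applied. Continuing paths were extended by another 41 per arm. The chi-square test at 0.05 was applied both to stopped trials and at the end. No treated infections with at least one placebo infection counts as a stop.

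| Common infection rate | No look | Ratio ≥ 3 | Ratio > 3 |
|---|---|---|---|
| 24% | 5.0% | 5.5% | 5.4% |
| 16% | 4.9% | 6.1% | 6.2% |
| 12% | 4.9% | 6.3% | 6.5% |
| 8% | 4.7% | 5.9% | 6.1% |

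On a finer grid of rates the maximum is 6.6%, at 11% under > 3. If at least one treated infection is required for a stop, the ranges are 5.0% to 6.1% (≥ 3) and 5.3% to 6.3% (> 3). With no true effect, the ≥ 3 rule stops the trial 1% of the time at a 24% rate and 13% at an 8% rate.

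**5. If 24% v 8% is true.**

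| | No look | Ratio ≥ 3 | Ratio > 3 |
|---|---|---|---|
| Chance of stopping at the look | – | 55% | 49% |
| Share of stops with p ≥ 0.05 | – | 12% | 5% |
| Chance of ending with p < 0.05 | 81.7% | 77.7% | 81.4% |
| Expected enrolment, 164 − 82 × P(stop) | 164 | 118.5 | 124.0 |

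**6. A standard boundary on the same design.** O'Brien-Fleming (|Z| ≥ 2.797 at the look, 1.977 at the end) gives type I error of 4.7% to 5.0% over the same four rates and power of 81.5%. The stop probability under 24% v 8% is 17.5%, so expected enrolment is 164 − 82 × 0.175 = 149.6 (about 150).

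**The case against.** The enumeration is exact but its inputs are partly assumed. The plan does not say that a stopped trial will be tested at the full 5%. If a stopped trial never claimed significance, the error would be 2.9% to 4.7%. A continuity-corrected test at both looks would give 1.7% to 3.6%. At the planned 24% rate the excess is only about half a point, and the larger figures need a lower common rate. Read as strictly more than 3, the rule costs almost no power (81.4% against 81.7%) and few stops are non-significant. The choice among boundaries is partly preference, and the oversight committee has its own power to close the study.

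Much of this stands as a limit on size. The excess is modest, and the power loss belongs to the ≥ 3 reading only. It does not remove the fault. Neither protective reading is written, and the continuity-corrected one conflicts with 82 per arm. In every case in step 4 the error is above its no-look value. Committee discretion does not soften a rule that says the study will be stopped. Treating the stop itself as proof of efficacy would give 5.6% to 15.9% under ≥ 3, but the plan does not say that and the conclusion does not rest on it.

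**Conclusion.** The concern holds and should be fixed. The trigger equals the design effect and has no test, event floor or alpha allocation, so the 5% claim is not supported. The error is 5.4% to 6.5% at the rates tabulated, or 5.0% to 6.3% if a stop needs at least one treated infection, against 4.7% to 5.0% with no look.

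The more practical fault is a mandatory stop on data that can fail the plan's own primary test. If ≥ 3 is meant, the chance of a significant result under the design rates also falls below the stated 80%.

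These sizes assume 41 per arm at the look, an uncorrected chi-square at 5% on both occasions, no attrition, and common infection rates between 8% and 24%. Confidence is high that the rule is deficient; the exact size depends on how it is read.

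**What to change.** Replace the ratio rule in Section 9.0 with a group-sequential boundary on the primary chi-square test. One example is O'Brien-Fleming: stop for efficacy only if the result favours treatment with |Z| ≥ 2.797 (two-sided p of about 0.005), and test the final analysis at |Z| ≥ 1.977 (p of about 0.048). Haybittle-Peto (p < 0.001 at the look, 0.05 at the end) also works, with type I error of 4.7% to 5.0%, power of 81.7% and a 7% chance of stopping under 24% v 8%. State how a stopped trial will be analysed, and report a bias-adjusted estimate if it stops early.

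Two clarifications would help, though neither is an error. Say that the look waits until the 82 treated patients have known 30-day infection status, and that the complication-rate review is a safety look under the committee's powers in Section 11.0.

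The change is a few sentences, and the maximum stays at 164. The costs, under 24% v 8% and compared with the ≥ 3 rule, are:

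- The chance of an early stop falls from 55% to about 18%.
- Expected enrolment rises from about 118 to about 150. Both figures ignore patients enrolled while 30-day outcomes are awaited.
- The average difference observed at a stop is more exaggerated, about 27 points against 21 (true value 16), which is why the adjusted estimate is needed.

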10.0 Privacy/Confidentiality Issues

Patients will be consented in a private hospital room setting in order to protect confidentiality.

11.0 Follow-up and Record Retention

Information stored in the database will be stored for an indefinite period of time for future reference, including for use in subsequent data analyses. Throughout the study, all collected data will be entered directly in to the secure password-protected web-based database. In terms of study purposes, we will plan to follow for a 90 day period. The 90-day post operative visit will be a telephone visit.

As stated in the informed consent document, participants' consent to use or share PHI does not expire unless study staff has been explicitly notified of this decision in writing from the participant (even in the event that a subject withdraws from further participation).

11.0 DATA SAFETY MONITORING PLAN

DSMP for Moderate Risk Trials (Level 2)

Moderate Risk Trials

Investigators will conduct continuous review of data and patient safety. **Monthly review meetings** for Phase I/II and Phase II trials are required and will include the principal investigator, clinical research specialist and/or research nurse (other members per principal investigator's discretion). **Monthly** meeting summaries will include review of data, the number of patients, significant toxicities as described in the protocol, and responses observed. Summaries will be submitted monthly and reviewed quarterly by the DSMC.

Study Auditing and Monitoring

All trials conducted at the IUSCC are subject to auditing and/or monitoring. Reports will be reviewed quarterly by the full DSMC (Reference Risk Table in full DSMC Charter).

Early Study Closure

At any time during the conduct of the trial, if it is the opinion of the investigators that the risks (or benefits) to the patient warrant early closure of the study, this recommendation will be made in writing to the Data Safety Monitoring Committee. Alternatively, the DSMC may initiate suspension or early closure of the study based on its quarterly review of the investigator reports.

Reporting Guidelines

The DSMC has streamlined the reporting process by utilizing reports from OnCore. This has allowed direct view of reports within the Clinical Trials Management System (CTMS); thus discontinuing paper reports. SAE reports are entered into OnCore monthly and reviewed by the DSMC chair and/or coordinator monthly. Findings will be reported to the full DSMC quarterly.

Reporting Death:

Death will be reported per local IRB reporting guidelines. The DSMC will review all reported deaths monthly.

Study Accrual Oversight

Accrual data will be entered into the IU Simon Cancer Center OnCore system on a monthly basis. The Protocol Accrual Committee (PAC) reviews study accrual twice per year while the PAC coordinator reviews accrual quarterly.

Protocol Deviations

Protocol deviations are entered into OnCore monthly and reviewed by the DSMC chair and/or coordinator monthly. Findings will be reported to the full DSMC quarterly.

12.0 References:

1. Yeo, C.J., et al., *Six hundred fifty consecutive pancreaticoduodenectomies in the 1990s: pathology, complications, and outcomes*. Ann Surg, 1997. **226**(3): p. 248-57; discussion 257-60.

13.0 APPENDICES

13.1 APPENDIX I-TOXICITY CRITERIA

NOTE: the attached Appendix I contains reference to the DCT/NCI Common Toxicity Criteria, Version 4.0, used to grade toxicities in reporting an "ADR" (adverse drug reaction) as described in Section 15.0 of this protocol. Other toxicity criteria (i.e., related to specialized treatments such as immunotherapy or BRMs) may be used as needed.

13.2 APENDIX II-CTMC CHECK SHEET

Appendix I
NCI Common Toxicity Criteria
Version 4.0

Due to the size of the latest version of the Common Toxicity Criteria, copies of this appendix are not included with this protocol document.

An electronic copy is available on the CTEP web site,
<http://ctep.cancer.gov/reporting/ctc.html>

Appendix II
CTMC Check Sheet

Meeting Date:			
Team/Program: (include meeting sign in sheet)			
Protocol & Status (open/closed to accrual)			
PI:			
CRS:			
	Y	N	N/A
Weekly and Monthly meetings should include discussion on data, patient safety, dose levels, accrual numbers, significant toxicities, dose adjustments and responses observed, deviation summaries and SAE reports. (per IUSCC DSMP)			
Has patient safety data been discussed/reviewed? Have all SAE's and deviations been reported in Oncore for all IUSCC programs.			
Has all data been entered into Oncore per the " Data Requirements for Cancer Center Reporting " SOP?			
Deviation Log reviewed, discussed and signed by ALL team members including PI			
Has accrual been entered into Oncore for all IUSCC programs per the " Data Requirements for Cancer Center Reporting " SOP			
*Notes
